**Sample size:**

We plan to recruit 130 women to ensure that we obtain full data for 80 subjects.

**Anticipated risks:**

This study has minor risks. There is a small risk of mild bruising, soreness or bleeding after the real acupuncture needle is withdrawn. There is a risk that participants may experience a negative reaction from acupuncture and thereby experience worse symptoms from participation in the study. Participants may feel mild discomfort upon needle insertion, but this dissipates once the needle has been inserted. To avoid or minimize these risks only experienced licensed acupuncturists will perform the acupuncture. There is a risk that some of the questions in the questionnaires may make the participants uncomfortable, nervous or tired, but they don't need to answer any question they don't wish to answer. There is also the risk of loss of privacy or confidentiality, but we will avoid this risk as much as possible.

**Anticipated benefits:**

There may be no benefit to individual subjects, but the knowledge gained from this study is expected to provide important insights to guide future research on initial and maintenance acupuncture treatment protocols for control of vulvodynia pain.

**Inclusion criteria:**

Potential participants must fulfill the following:

- a) a previous diagnosis of generalized vulvodynia or provoked vestibulodynia
- b) 18 to 45 years old
- c) a pain now score 4 or higher with tampon insertion and removal performed at the initial screening exam
- d) speak and read English

**Exclusion criteria:**

Potential participants will be excluded if any of the following is true:

- a) infectious conditions
- b) inflammatory conditions
- c) neoplastic disorders
- d) neurologic disorders
- e) trauma to the genitals
- f) iatrogenic
- g) hormonal deficiencies
- h) co-morbid pelvic pain conditions (to avoid confounding pain outcomes)
- i) pelvic inflammatory disease
- j) endometriosis
- k) menopause
- l) pregnancy
- m) women receiving concurrent therapies that may decrease stress and/or muscle tension (i.e., concomitant physical therapy, biofeedback, massage, or other acupuncture sessions) will also be excluded

**Data collection and management:**

Some of the research data will be collected electronically using a laptop computer. The PAINReportIt computerized pain assessment program developed by [name] to collect subjects' pain information will be completed online. Subjects' data will be written directly to the College of Nursing server and will not reside, even temporarily, on the laptop computer. HTTPS will be used for data transfer to the CON server and the transfer from the tablet to the server is encrypted. The application will be located in a secure College of Nursing server with restricted access, with access only to the immediate study

**Title: DOUBLE-BLIND PHASE 2 RCT: EFFECT OF ACUPUNCTURE ON PATIENT VULVODYNIA OUTCOMES**

**RESEARCH PROTOCOL**

Dated 8/15/2017

personnel. The other questionnaires (Female Sexual Function Index (FSFI), Vulvar Pain Functional Questionnaire, and the Double-Blind Needle Questionnaire) will be completed on paper.

All participants will be assigned a code number and their data will be identified only with that code number. The link of the code numbers to the subject identifiers will be kept separate from the study data. Only the investigators and key personnel will have access to the code/master key. The computerized data will be stored in a controlled access computer database in a secure College of Nursing server. All hard data collected will be stored in a locked office in the College of Nursing.

Data management procedures will be supervised by [name], the statistician.

**Data analysis:**

[name] will supervise all data analysis procedures. Prior to data collection and entry, a codebook will be created with the variable names, descriptions, and value codes of each variable. Missing data will be minimized through our retention efforts but are inevitable, to some degree, in any longitudinal study. We will address missing data by intention to treat analyses (ITT), using the full information maximum likelihood (FIML) approach, which has been shown to produce unbiased parameter estimates and standard errors. To begin to phenotype subjects with emotional disturbances we will explore the emotional dimension of pain at baseline and after the 10th acupuncture treatment using the well-known Pain Rating Index-Affective (PRI-A) score from PAINReportIT®.

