**Title: DOUBLE-BLIND PHASE 2 RCT: EFFECT OF ACUPUNCTURE ON PATIENT VULVODYNIA OUTCOMES**

**RESEARCH PROTOCOL**

Dated 8/15/2017

Specific aims are to:

Aim 1. Compare the penetrating needle group and the skin touch placebo needle group for effects on the: (a) primary outcome: vulvar pain (PAINReportIt® average pain intensity, 0-10), and (b) secondary outcomes: dyspareunia (FSFI dyspareunia) and sexual function (FSFI total). We hypothesize that controlling for baseline values, at posttest there will be statistically significant less vulvar pain (primary) and dyspareunia and better sexual function in the penetrating needle group compared to the skin touch placebo group.

Aim 2. In subjects with a clinically meaningful reduction in pain intensity (at least 1.5 points) at posttest compared to pretest, describe the duration of the acupuncture treatment and placebo effects weekly until pain returns to pretest or up to 12 weeks after posttest. We will describe the variability over time in vulvar pain intensity (0-10) after a tampon insertion-removal stimulus and thereby explore the duration of the effect by intervention group, vulvodynia subgroups, and demographic subgroups (e.g., age, race, occupation). These findings will provide insights to guide future research on initial and maintenance acupuncture for vulvodynia.

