**Title: DOUBLE-BLIND PHASE 2 RCT: EFFECT OF ACUPUNCTURE ON PATIENT VULVODYNIA OUTCOMES**

**RESEARCH PROTOCOL**

Dated 8/15/2017

sham procedure to mask both the acupuncturist and subject to the type of needle used. The acupuncturist will be well-trained in the study protocol and will be observed for fidelity. We will obtain measures at 2 time points (baseline and immediately post 10th acupuncture treatment [5 weeks]). Duration of effects will be measured weekly beginning one week after posttest for up to 12 weeks.

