**Title: DOUBLE-BLIND PHASE 2 RCT: EFFECT OF ACUPUNCTURE ON PATIENT VULVODYNIA OUTCOMES**

**RESEARCH PROTOCOL**

Dated 8/15/2017

however, are regular needles used in routine acupuncture. All participants will be informed that they will receive either real or fake acupuncture and they will not be told what kind of needles they are receiving until they complete the duration of effect portion of the study. Participants in the control group will be offered 10 free real acupuncture sessions with regular (not double-blind) acupuncture needles administered by a second acupuncturist after the end of the 17 weeks. The double blind needles are manufactured by [name], the inventor of the double blind acupuncture needle, and will be sent to us sterilized and packaged to maintain sterility.

All participants will receive 10 acupuncture session, two sessions per week over an approximately 5 week period. Each session will last about one hour. The first and last sessions only, where participants will complete the study questionnaires, are expected to last an additional 30 - 60 minutes. Each acupuncture treatment will consist of 13 acupuncture points, of which 12 points specifically treat problems with the genitals. Once the 13 needles are inserted or placed on the skin in the 13 points, they will remain in place for 45 minutes. The RS will remain with the subjects during the treatment session.

At pre-test, before the first acupuncture session, and at post-test, after the 10th acupuncture treatment, participants will be asked to insert and remove a regular Tampax™ tampon with applicator as a standardized pain stimulus, and will complete the three study measures of vulvar pain and sexual function on a computer or tablet:

- 1) PAINReportIt® computerized program to assess pain intensity as well as collect demographics and medications information
- 2) Female Sexual Function Index (FSFI) to assess dyspareunia and sexual function
- 3) Vulvar Pain Functional Questionnaire to describe the physical dimension of impairment in women with vulvodynia
- 4) At post-test, participants will also complete the Double-Blind Needle Questionnaire for the participants to report whether or not they remained blinded to the type of needle used (penetrating or skin touch placebo).

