Weekly for up to 12 weeks after the 10th treatment session, the subjects will be asked to insert and remove a regular Tampax™ tampon with applicator from their vagina and complete the weekly vulvar pain diary to record their vulvar pain, so that we can determine the duration of the treatment effects.

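### No posttest is described for women who stop before session 10, and FIML is called unbiased without its missing-at-random condition or a sensitivity analysis

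*Combined protocol and SAP*

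**What the plan says.** - **Timing of measures.** Study design: "We will obtain measures at 2 time points (baseline and immediately post 10"th "acupuncture treatment [5 weeks"]). Procedures repeats this: "At pre-test, before the first acupuncture session, and at post-test, after the" tenth treatment, "participants will be asked to insert and remove a regular Tampax" tampon and complete the questionnaires. The follow-up diary has the same anchor: "Weekly for up to 12 weeks after the 10"th session.
- **Schedule.** Procedures gives "two sessions per week over an approximately 5 week period", so session 10 and week 5 coincide only roughly.
- **Early stopping.** The one case described is a positive pregnancy test, after which the woman's participation ends (Procedures). Nothing is said about her outcome data.
- **Primary comparison.** Specific aims: "We hypothesize that controlling for baseline values, at posttest there will be statistically significant less vulvar pain" in the penetrating needle group.
- **Missing data.** The Data analysis section says that some loss cannot be avoided, refers to retention efforts, and commits to intention to treat "using the full information maximum likelihood (FIML) approach, which has been shown to produce unbiased parameter estimates and standard errors". It names no variables for the model, states no assumption about why data are missing, and plans no sensitivity analysis.

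**The concern.** Followed as written, the plan leaves a woman who stops at, say, session 4 with a baseline value and nothing else. The intention-to-treat label then rests wholly on the missing-data method, and that method is presented as unbiased without conditions.

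An unstated assumption matters most where the data can least support it. With only two measurement times, no intermediate pain score shows how a woman was doing before she left. If leaving is related to the pain she would have reported at posttest, and this works differently in the two arms, the primary effect is biased. The direction depends on the arm. A posttest that was never sought cannot be recovered afterwards, and a sensitivity analysis carries most weight if it is fixed before unblinding.

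**Working it through.** **1. What the documents supply.** There is no loss rate, SD or effect size. The only related figure is 130 women recruited to give 80 with full data: (130 − 80)/130 = 38.5%. The recruitment section says this covers screening as well as attrition. Loss after randomisation could therefore lie anywhere from 0% (80 randomised) to 38.5% (130 randomised). The figure is a ceiling and is not used below.

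**2. What FIML does with this design.** Let b be baseline pain, y posttest pain and g the arm. The likelihood factors as f(b) × f(y | b, g). A woman with no y contributes only f(b), which contains no parameter of the adjusted arm effect. The maximum-likelihood arm effect is therefore the ANCOVA estimate from women who have a posttest. Numerical check on one simulated trial (130 women, 24 posttests missing, 14 placebo and 10 needle): both methods gave −1.119063, equal to 6 decimals, with or without an arm difference at baseline. Only the equality matters here. Auxiliary variables in the model could change the result somewhat, but the plan names none.

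**3. How a departure from missing at random carries over.** If missing women are worse than FIML predicts by δ points, and m is the fraction missing, then

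shift in (needle − placebo) = m_needle × δ_needle − m_placebo × δ_placebo.

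Take δ = 1.5, the plan's own threshold for a meaningful reduction, in one arm only. The shift is 0.10 × 1.5 = 0.15 points at 10% missing in that arm and 0.20 × 1.5 = 0.30 at 20%. With equal m and equal δ in both arms it is 0.

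**4. Illustrative size.** All inputs are assumptions: true benefit 1.0 point; residual SD and baseline SD 1.8; baseline slope 0.5; log-odds of loss 0.4 to 0.8 per point of posttest pain; overall loss 10% or 20%. Each cell is completers ANCOVA on 600,000 simulated women, mean of 3 runs (SD between runs at most 0.012). Ranges run from log-odds 0.4 to 0.8.

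| Loss process | 10% loss | 20% loss |
|---|---|---|
| One common pain-related model, so loss is unequal by arm | 0.96 to 0.89 | 0.93 to 0.84 |
| Pain-related in needle arm only, equal loss | 1.12 to 1.21 | 1.24 to 1.39 |
| Pain-related in placebo arm only, equal loss | 0.88 to 0.79 | 0.76 to 0.62 |
| Same relation and equal loss in both arms | 1.00 | 1.00 |
| Depends on baseline pain only (missing at random) | 1.00 | 1.00 |

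In the first row, loss in placebo versus needle is 11.7% v 8.3% to 12.8% v 7.2% at 10% overall, and 23.0% v 17.1% to 24.7% v 15.4% at 20%. Independent reruns agreed to within about 0.015.

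With residual SD varied from 1.5 to 2.2, the first row becomes 0.97 to 0.87 / 0.95 to 0.79 and the second 1.09 to 1.29 / 1.17 to 1.53.

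**5. Other assumptions, same pattern.** With true effect −1.5, SD 2, baseline–posttest correlation 0.5 and about 15% to 29% missing per arm, the estimates were −1.50 (missing at random), −1.40 (common pain-related model), −1.24 (placebo arm only) and −1.66 (needle arm only).

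**6. No true effect.** Under one common model the two arms then have the same posttest distribution, hence equal loss and no bias. In the needle-only case with loss fixed by arm, a constant shift in pain is absorbed by the intercept of the loss model, so the overstatement (for example 1.24 − 1.00 = 0.24) remains.

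**The case against.** The strongest reply is that silence is not prohibition. The 5-week label, the intention-to-treat commitment and the retention efforts could be read as covering every randomised woman. That is fair. A reader might infer that the plan excludes women who stop early, or that ending participation after a positive pregnancy test contradicts intention to treat. Neither follows. The procedure is under-described, and a woman who leaves can stay in the analysis set with her baseline value. What remains open is whether her posttest is sought. Parts of the document were also not available to this review.

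Second, the FIML sentence may be shorthand, since any user of the method knows the condition. Adding the condition by itself changes no analysis. The substance lies in the unsought posttest and the absent sensitivity analysis.

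Third, the equality with completers ANCOVA is conditional. Baseline sexual function, functional impairment and affective pain scores are collected and could enter as auxiliary variables. This limit stands, although auxiliaries missing at the same posttest would help little.

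Fourth, the larger biases need pain-related loss in one arm and random loss in the other. If masking of participant and acupuncturist holds, this is less likely, though not impossible. Under the common model, bias only shrinks a real benefit, and it creates none where none exists.

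Finally, a tipping-point analysis cannot reveal the mechanism either. That is true, and it is not offered for that purpose.

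**Conclusion.** The point holds as a gap that should be closed. Two facts rest on the text itself: no primary-outcome assessment is described for women who stop before session 10, and FIML is called unbiased with neither its condition nor a sensitivity analysis. Confidence in these is high.

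The size of any bias is unknown. On the assumed inputs it ranges from none, through a modest dilution under a common loss process, to an overstatement of 0.12 to 0.39 points if pain-related loss is confined to the needle arm. A reader might infer that the primary result will be biased, or that 38.5% dropout is planned. The documents support neither: several plausible loss processes give no bias, and the 50 women include screening failures. Nor is FIML a wrong choice. It is valid under missing at random with a correct model, and the plan should say so.

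**What to change.** 1. **Collect.** Seek the posttest at about week 5 from all randomised women, whatever number of sessions they received. For those who complete, this is after session 10 within a stated window; for those who stop, at the corresponding time. It needs consent, and the investigators must consider the assessment appropriate, since it includes the tampon stimulus. Analyse as randomised. Clarify whether ending a woman's participation also ends outcome data collection, without changing any treatment-stopping rule.
2. **State.** Write that FIML is unbiased if data are missing at random and the model is correct. Include vulvodynia type (the randomisation stratum in Study design) and baseline pain in the model.
3. **Test.** Prespecify, before unblinding, one delta-adjusted tipping-point analysis of the primary outcome with the shift varied separately by arm. It shows how far departures from missing at random would have to go to change the conclusion, not which mechanism holds.

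The cost is some protocol wording, effort to contact women who stop, and a little more analysis. Some will decline or be unsuitable for the assessment, so some posttests will still be missing.

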**Study design:**

We will conduct a pretest/posttest, randomized, placebo controlled phase 2 efficacy study on 130 subjects with vulvodynia, with high scientific rigor. In this adequately powered study, we will compare two groups (penetrating acupuncture needle [treatment] group and skin touch needle [placebo] group) in a 13-needle, 10-session acupuncture protocol delivered twice/week for 5 weeks for effects on vulvar pain (primary outcome), and dyspareunia and sexual function (secondary outcomes). Subjects will be stratified by type of vulvodynia (generalized or provoked) and randomized 1:1 either to the penetrating needle group or the skin touch placebo needle group. These double-blind needles will provide a strong

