**Subject identification, recruitment and consent:**

The subjects will be women with a diagnosis of vulvodynia, who are 18 – 45 years of age. Potential participants will be recruited from clinical and community settings in Chicago, such as the UIC campus and surrounding communities, gynecologists, certified nurse-midwives, family physicians, and women's health physical therapy practices. Recruitment will also be conducted via a link on the National Vulvodynia Association (NVA) website. We will also recruit through social media like Facebook, in addition to through phone calls and emails. We plan on recruiting up to 130 women to ensure that we have full data on 80 subjects after screening and attrition. We will strive to enroll a racially and ethnically diverse sample of women.

The consent process will be completed at the UIC College of Nursing. It may also be completed at another UIC or other private location chosen by the potential subject to go over the details of the study and informed consent. All study procedures will be conducted at the UIC College of Nursing in fully equipped, clinical research exam rooms on the second floor. The screening gynecological screening exam will take place in one of the exam rooms in the CON or at [name] office in the UIC hospital.

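### The plan calls FIML standard errors unbiased without qualification; at the planned 80 women, uncorrected ones are about 2% too small, which may lift a nominal 5% test by up to about one percentage point

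*Combined protocol and SAP*

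**What the plan says.** The Data analysis section is the only place where an estimation method is named. It places the handling of incomplete data under the intention-to-treat principle and gives the estimator and its justification as follows: "using the full information maximum likelihood (FIML) approach, which has been shown to produce unbiased parameter estimates and standard errors". No sample-size condition is attached, and the section mentions no restricted likelihood, t reference, degrees-of-freedom correction, robust standard error or bootstrap.

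The planned size is given under Sample size: "We plan to recruit 130 women to ensure that we obtain full data for 80 subjects". The recruitment section says the same and adds that the loss covers both screening and attrition.

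Aim 1 sets the comparison: "We hypothesize that controlling for baseline values, at posttest there will be statistically significant less vulvar pain". It therefore needs a baseline-adjusted test between the arms. The Study design section adds one stratification factor: "Subjects will be stratified by type of vulvodynia (generalized or provoked) and randomized 1:1".

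The plan gives no alpha, sidedness, model equation, test statistic or reference distribution.

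**The concern.** Under maximum likelihood the residual variance estimate divides by n and ignores the mean parameters that were fitted. The resulting standard error is biased downwards in finite samples, even when no data are missing. The issue is therefore separate from whether data are missing at random, and it leaves the treatment estimate itself unaffected. If the standard error is then paired with a normal reference, a second and separate source of optimism is added, because a t reference would be wider.

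Aim 1 rests on a statistically significant difference. A test that rejects slightly too often under the null, with an interval slightly too narrow, would overstate the evidence a little. The stated justification would also lead a reader to think that no correction is needed at this sample size.

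**Working it through.** **Inputs from the documents.** 80 women with full data, out of up to 130 recruited; 1:1 allocation; two time points for the primary comparison; baseline adjustment; one binary stratification factor.

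**Assumptions, because the documents are silent.** Two-sided alpha of 0.05. Normal linear model with p = 3 mean parameters (intercept, arm, baseline), or p = 4 with vulvodynia type added.

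**The plan's own figure.** The plan states no type I error rate that could be reproduced. The sample sizes imply a combined loss of 1 - 80/130 = 38.5%. This is back-calculated from the two numbers, so it does not check them independently.

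**Step 1: standard error.** The ratio of the ML standard error to the one based on the unbiased variance estimate is sqrt((n - p)/n).
- n = 80, p = 3: sqrt(77/80) = 0.9811, or 1.9% too small.
- n = 80, p = 4: sqrt(76/80) = 0.9747, or 2.5% too small.

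This step needs no assumption about alpha or the test.

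**Step 2: actual level of a nominal 5% test.** With ML standard errors and critical value c, the level is 2·P(t with n - p df > c·sqrt((n - p)/n)). A likelihood-ratio test rejects when n·ln(1 + t²/(n - p)) > 3.841.

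| Test, n = 80 | p = 3 | p = 4 |
|---|---|---|
| ML standard error, t reference | 5.44% | 5.59% |
| Unbiased variance, z reference | 5.36% | 5.37% |
| Likelihood-ratio, chi-square reference | 5.53% | 5.69% |
| ML standard error, z reference (Wald z) | 5.82% | 5.99% |

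The first two rows separate the causes. The standard error alone gives 5.4-5.6%; the rest of the Wald z excess comes from using z in place of t.

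**Step 3: more posttests than 80.** Wald z with ML standard errors gives 5.65% (p = 3) and 5.78% (p = 4) at n = 100, and 5.49% and 5.59% at n = 130.

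**Step 4: simulation, 200,000 null trials per setting.** Wald z with ML standard errors rejected in 5.82% (n = 80, p = 3) and 5.90% (n = 80, p = 4). With 130 women and 38.5% of posttests missing completely at random (p = 3), it rejected in 5.84%. Women with a baseline value only therefore do not remove the problem: for the posttest given baseline and arm, FIML reduces to ML on the women who have a posttest. With the residual-df variance and a t reference, the same three settings gave 4.98%, 4.91% and 4.97%.

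**Step 5: interval width at n = 80.** Wald z relative to the t interval:
- p = 3: 1.96 × 0.9811 / 1.9913 = 0.966, or 3.4% too narrow.
- p = 4: 1.96 × 0.9747 / 1.9917 = 0.959, or 4.1% too narrow.

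**The case against.** The strongest objection is that the criticised test is not in the plan. FIML is named as the way to handle missing data, and no model, statistic or reference distribution follows. An analyst could use a t reference or a small-sample correction without departing from the text. On this view the sentence is a loosely worded justification that lacks the word asymptotically. The effect is also small: with Wald z and 80 posttests, the conclusion changes only if the properly calibrated p-value lies between 0.05 and about 0.06.

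Most of this stands, and it rules out several stronger readings.

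- A reader might infer that the primary test will run at 5.8-6.0%. The documents do not support that as a fact. It requires a two-sided 5% level, a z reference, 3 or 4 mean parameters and exactly 80 posttests, and the plan fixes none of the first three. Eighty is a target for full data, and more posttests would lower the figure.
- A reader might attribute the whole excess to the standard errors. They account for 5.4-5.6% only.
- A reader might expect much larger inflation in small subsets. No hypothesis test in a smaller subset is planned: the responder and subgroup work in Aim 2 is to describe and explore duration. Fewer usable FSFI scores are possible, since participants may decline questions, but no such number is planned.

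What the objection does not remove is the sentence itself. It claims unbiased standard errors without condition, and nothing else in the plan supplies a correction. Every uncorrected ML version computed here exceeds 5%.

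**Conclusion.** The point holds as a minor one. The statement on standard errors is wrong as written for a trial of this size. The shortfall is 1.9% to 2.5% at 80 women, assuming a normal linear model with 3 or 4 mean parameters.

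The consequence for the test is conditional on an assumed two-sided 5% level and on an implementation that the plan does not name. Across the uncorrected ML options the level at 80 posttests runs from 5.4% to 6.0%, an excess of at most about one percentage point. That would matter only for a borderline primary result. It is no reason to doubt the treatment estimate or to abandon likelihood handling of missing posttests.

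**What to change.** - Fit the baseline-adjusted pretest/posttest model by restricted maximum likelihood with Kenward-Roger degrees of freedom. This keeps the likelihood handling of missing posttests. ANCOVA with the residual-df variance and a t reference is an acceptable alternative for the two-time-point comparison.
- State alpha, sidedness, the model terms (including whether vulvodynia type is included) and the reference distribution.
- Reword the justification so that unbiased standard errors are described as a large-sample property.

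The cost is a sentence or two in the Data analysis section and a software option. At 80 posttests the interval becomes wider than the Wald z interval by 1/0.966 = 1.04 (p = 3) or 1/0.959 = 1.04 (p = 4), so about 4%. The simulated level returns to 4.9-5.0%.
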